6.4.2 Randomization and Hemostat Application

At the start of each surgical procedure, a single HEMOBLAST™ device and a single G+T device will both be prepared per the respective Instructions for Use (unless the subject is a lead-in subject; all lead-in subjects will have a single HEMOBLAST™ device prepared). The preparation time for both devices will be recorded for the TTH Population subjects.

Randomization will be performed through sequentially numbered sealed envelopes. Four-hundred subjects (TTH Population) will be randomized to receive HEMOBLAST™ or G+T in a 2:1 ratio:

- 267 subjects will be randomized to receive HEMOBLAST™; and
- 133 subjects will be randomized to receive G+T.

There will be a maximum of 50 lead-in subjects; these subjects will not be randomized. The first subject for each investigator will be treated as a lead-in subject. These subjects will receive HEMOBLAST™ and will be followed for safety only (maximum Full Analysis Population of 450); lead-in subjects will not count towards the TTH Population. Please see Section 12 below for additional detail on subject populations.

Randomization will be stratified by surgical indication and will incorporate blocking; additional details of randomization and blocking will be included in a separate Randomization Plan.

After randomization and enrollment, the assigned hemostat will be used in the investigational subject; the other hemostat will be discarded following institutional procedures.

A study-specific stopwatch will be used to track hemostat application and the times of hemostasis evaluation. The time of initial hemostat application will be considered time 0; at this time, the stopwatch will be started by the study coordinator. The stopwatch will run continuously without stopping.

Hemostasis will be evaluated by the investigator at the following time points until hemostasis has been achieved:

- 3 minutes;
- 6 minutes; and
- 10 minutes.

Reapplication of the randomized hemostat will be performed at the 3 minute and 6 minute evaluation time points, as described below.

For cardiothoracic procedures, the TBS will be identified after heparin reversal. Additionally, the TBS will not be at the site of a valve implant or at the site of a synthetic graft or patch implant.

HEMOBLAST™ will be applied according to its instructions for use.

1. Peel open the pouches to remove contents with attention to sterile procedures.
2. Remove cap using a twisting motion.

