6.4.5 Intraoperative Data Collection

The following data will be recorded on the Intraoperative CRF:

- Surgical procedure(s);
- Preparation times for each device;
- Description of TBS;
 - Location,
 - Tissue type,
 - Conventional means for hemostasis (pressure, suture, cautery, etc.),
- Confirmation of intraoperative eligibility criteria;
- Approximate dimensions of target bleeding site;
- SBSS score at baseline and each evaluation time point (3, 6, and/or 10 minutes) until hemostasis is achieved;
- Randomization;
 - Randomization envelope number,
 - Time of randomization,
 - Treatment arm and device lot/batch number data,
- Hemostat application;
 - Application amount
 - HEMOBLAST™ application amount will be approximated by indicating the amount of powder left in the bellows after application
 - G+T application amount will be documented by approximating the dimensions of Surgifoam sponge applied
- Rescue treatment(s), if any;
- Use of other hemostatic agent(s), if any;
- Skin open and skin closure times;
- Intraoperative administration of blood products;
- Total intraoperative estimated blood loss;
- Incidence of any device deficiencies; and

- Incidence of any complications or adverse events.

The Concomitant Medication, Adverse Event, and Device Deficiency CRFs will be completed as applicable.

Table 7 below shows a timeline of intraoperative procedures.

Table 7. Timeline for Intraoperative Procedures*

Time Point (Minutes:Seconds)	Study Procedures or Assessments
Prior to 00:00	
 • Prepare both hemostatic devices and record time of preparation • Identify Target Bleeding Site (TBS) • Assign SBSS score • Perform randomization (unless lead-in subject)
00:00	
 • Start stop-watch • Apply HEMOBLAST™ or G+T
03:00	
 • Assign SBSS score 
If SBSS = 0
 
 • Intraoperative efficacy evaluation completed 
If SBSS is NOT 0
 
 • Re-apply HEMOBLAST™ or G+T
06:00	
 • Assign SBSS score 
If SBSS = 0
 
 • Intraoperative efficacy evaluation completed 
If SBSS is NOT 0
 
 • Re-apply HEMOBLAST™ or G+T

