12.2.1 Analysis Populations

Safety analyses will be performed on the Full Analysis Population, defined as all subjects who were randomized into the study and received study intervention and all lead-in subjects. Efficacy analyses will be conducted on the time to hemostasis (TTH) Analysis Population, defined as all subjects who were randomized, received study intervention, and had a TTH assessment recorded regardless of whether the measurement was censored (defined as the use of an additional hemostatic product or surgical rescue prior to the end of observation time, or failing to achieve and maintain complete hemostasis prior to the end of observation time). Data summaries will be based on the intervention received, regardless of which intervention was randomly assigned.

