12.2.4 Accounting for Multiple Comparisons

The primary analysis comparing the probability of TTH within 6 minutes in subjects receiving HEMOBLAST™ to those receiving G+T will be conducted to maintain an overall 0.025 (one-sided) significance level accounting for one interim analysis and one final analysis (see Sections 12.4.1 and

12.4.2). The exclusion of a >10% difference in the probability of TTH at 6 minutes will be indicated by the lower limit of a 95% confidence interval for the adjusted difference in binomial proportions (HEMOBLAST™ – G+T). All reported inference (confidence intervals and p-values) will account for the planned interim analysis.

Adjustment for multiple comparisons when assessing secondary endpoints will be performed using a fixed sequence closed testing procedure. The experiment-wise Type I error rate will be controlled in the strong sense at a (two-sided) 5% significance level. In a fixed sequence testing procedure, the formal inferential testing can proceed to the next step only when statistical significance is declared in the current step. If the testing sequence is stopped, the remaining endpoints in the testing sequence will be considered exploratory. Furthermore, any comparisons that are not presented in the a priori specified testing procedure will also be considered exploratory. The fixed sequence testing procedure will be employed among the primary and secondary endpoints in the order presented below:

- 1) Primary endpoint: Success at achieving hemostasis within 6 minutes for the first treated bleeding site (comparable efficacy of HEMOBLAST™ relative to G+T, evaluated using a 10% non-inferiority margin);
- 2) Secondary endpoint: The difference between arms in mean preparation time, defined as the time from the opening of package to product being ready to use (measured in minutes and seconds);
- 3) Secondary endpoint: Success at achieving hemostasis within 3 minutes for the first treated bleeding site (comparable efficacy evaluated using a 10% non-inferiority margin);
- 4) Secondary endpoint: Success at achieving hemostasis within 6 minutes for the first treated bleeding site (superiority of HEMOBLAST™ relative to G+T); and
- 5) Secondary endpoint: Success at achieving hemostasis within 3 minutes for the first treated bleeding site (superiority of HEMOBLAST™ relative to G+T).

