12.2.6 Subject Disposition and Characteristics

The number of subjects randomized to each treatment arm will be tabulated and a flow diagram describing the disposition of subjects will be constructed. Demographic variables will include age (continuous and by age category [categorized by decade of life]), sex, race, ethnicity, height, and weight. Baseline disease characteristics will include reason for surgery and related co-morbidities. All continuous endpoints will be summarized using descriptive statistics, that will include the number of subjects (n), mean, standard deviation, median, minimum, and maximum. All categorical endpoints will be summarized using frequencies and percentages.

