12.3.1.2 Methods of Analysis

The primary efficacy endpoint is the difference in the probability of TTH within 6 minutes comparing HEMOBLAST™ to G+T. The lower bound of the 95% confidence interval for the difference in binomial probabilities will be used to assess comparable efficacy. The primary efficacy analysis will be conducted on data from the first identified bleeding site for each subject. The estimated difference in the probability of TTH at 6 minutes between treatment arms will be adjusted for surgical indication by weighting the stratum-specific differences in observed proportions using Cochran-Mantel-Haenszel weighting.¹⁸ The trial seeks to establish comparable efficacy based upon a non-inferiority margin of 10% for the difference in the probability of TTH within 6 minutes comparing HEMOBLAST™ to G+T (HEMOBLAST™–G+T). Letting θ denote the true difference in the probability of hemostasis at 6 minutes between HEMOBLAST™ to G+T, the trial will test the null hypothesis $H_0: \theta \leq -0.10$ vs. the alternative hypothesis $H_A: \theta > -0.10$ using a one-sided level 0.025 test. The null hypothesis of inferiority will be rejected and comparable efficacy will be established if the resulting lower bound of the 95% confidence interval for θ is greater than -0.10. Comparable efficacy will be evaluated using a group sequential testing design as described in Section 12.4 with stopping boundaries defined to ensure a maximum overall 1-sided significance level of 0.025. Following the completion of the trial, a confidence interval for the estimated difference in the probability of hemostasis at 6 minutes will be computed using the Cochran-Mantel-Haenszel estimator and asymptotic variance estimate in combination with the repeated confidence interval method.¹⁹ Estimates of the distribution of TTH over a maximum follow-up of 10 minutes will be computed based on all available assessment times (3 minutes, 6 minutes, and 10 minutes) using the Kaplan-Meier method.

Analyses of the secondary efficacy endpoints will be evaluated only once, at the end of the study, using a family-wise 2-sided significance level of 0.05. Adjustment for multiple comparisons when assessing

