8.3 Blinding

8.4 Subjects will be blinded to treatment assignment. Sample Size Considerations

The sample size for the proposed study is based on a level 0.025 (one-sided) test to exclude a probability of TTH within 6 minutes that is 10% less among subjects treated with HEMOBLAST™ compared to those

treated with G+T. The maximum number of subjects enrolled will be computed as to provide approximately 80.1% power to declare comparable efficacy when the two treatments have the same probability of TTH within 6 minutes. The variance estimate in the sample size calculation assumes an 88% 6 minute hemostasis success rate in both the HEMOBLAST™ and G+T arms. The planned stopping rule will implement a single interim analysis after outcome data have been observed on 240 treated subjects. If the study were to continue to the final analysis with a decision in favor of comparable efficacy, it is anticipated that efficacy data would be available on 400 treated subjects (approximately 267 patients treated with HEMOBLAST™ under a 2:1 randomization scheme). Assuming equal accrual to each surgical indication this would provide efficacy data on roughly 89 subjects treated with HEMOBLAST™ for each surgery type.

The variance of a proportion is dependent on the proportion itself. Hence, power for the study will be partially determined by the probability of TTH within 6 minutes on each of the treatment arms. Under the design assumption that the probability of TTH within 6 minutes on the G+T arm is 88%, the study will require a maximum of 400 treated subjects to attain approximately 80.1% power to declare comparable efficacy based upon a 10% non-inferiority margin. In order to maintain approximately 80.1% power should a larger variance be observed, a flexible sample size based on statistical information from pooled trial data will be used.¹

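### The only stated grouping rule is by device received, and no as-randomized analysis of the primary non-inferiority endpoint is planned

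*Protocol*

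**What the plan says.** Protocol 12.2.1 and SAP 10.2 assign the safety analyses to the Full Analysis Population. They assign the efficacy analyses to the TTH Population: subjects randomized, treated and with a recorded TTH assessment. Both paragraphs then close with one grouping rule, not limited to safety: "Data summaries will be based on the intervention received, regardless of which intervention was randomly assigned".

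Protocol 12.2.4 and SAP 10.10 introduce the primary test as "The primary analysis comparing the probability of TTH within 6 minutes in subjects receiving HEMOBLAST™ to those receiving G+T". The methods sections (Protocol 12.3.1.2, SAP 10.5.2) use a different term: "The estimated difference in the probability of TTH at 6 minutes between treatment arms will be adjusted for surgical indication". They do not say whether an arm means the device assigned or the device received.

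In reporting, randomized assignment is explicitly used only for disposition: "The number of subjects randomized to each treatment arm will be tabulated" (Protocol 12.2.6, SAP 10.3).

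On conduct, Protocol 6.4.2 has both devices prepared for each randomized case. After randomization, "the assigned hemostat will be used in the investigational subject; the other hemostat will be discarded following institutional procedures". SAP 8.2 places randomization just before treatment. On blinding, the SAP says only "Subjects will be blinded to treatment assignment".

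**The concern.** Randomization protects the comparison only if outcomes are counted in the arm to which subjects were assigned. Here a switch could be related to prognosis. The bleeding score is assigned before the envelope is opened (Protocol 6.4.5, Table 7), both devices are ready, and nothing says the surgeon is blinded. If a surgeon gives the other device because a bleed looks difficult, grouping by receipt takes a likely failure out of one arm and adds it to the other. The non-inferiority estimate can then be biased in either direction.

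Protocol 12.1.4 defines overall study success by this comparison alone. The envelope records, disposition counts and deviation summaries would show that switches had occurred, but they would not give the as-randomized estimate. Choosing a grouping after seeing the switches would be post hoc.

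**Working it through.** **Is there an as-randomized analysis elsewhere?** The planned supporting analyses of the primary endpoint are:
- a worst case for missing data (SAP 9.2);
- a normal-coagulation subset and a worst case for abnormal coagulation (Protocol 12.2.3, SAP 10.9);
- site-pooling models (SAP 9.4).

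None is stated to regroup subjects by assignment.

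**The plan's own figure.** Inputs from Protocol 12.4.1 and Table 9: 88% success in both arms; 10-point margin; one-sided 0.025; 160/80 subjects at the interim and 267/133 at the end; efficacy boundaries 2.373 and 2.036; futility boundary 0.788. With unpooled variance, SE = sqrt(0.88 × 0.12 × (1/n_H + 1/n_G)). A two-look normal calculation gives power of 80.0% with futility applied and 81.4% with it ignored, against the stated 80.1%. Type I error with non-binding futility is 0.0250. The design reproduces, and these figures do not depend on the grouping rule when nobody switches.

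**Shift in the by-received difference when there is no true difference.** Assume k subjects switch and each fails with probability f on either device, with 88% success in each randomized arm.

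- HEMOBLAST-assigned given G+T: (0.88×267 − k(1−f))/(267−k) − (0.88×133 + k(1−f))/(133+k), which equals k(f − 0.12)[1/(267−k) + 1/(133+k)].
- G+T-assigned given HEMOBLAST: −k(f − 0.12)[1/(267+k) + 1/(133−k)].

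Example with k = 4, f = 0.5: 4 × 0.38 × (1/263 + 1/137) = 1.69 points.

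| Direction | f | k = 2 | k = 4 | k = 6 |
|---|---|---|---|---|
| HEMOBLAST to G+T | 1.0 | +2.0 | +3.9 | +5.8 |
| HEMOBLAST to G+T | 0.5 | +0.8 | +1.7 | +2.5 |
| G+T to HEMOBLAST | 1.0 | −2.0 | −4.0 | −6.1 |
| G+T to HEMOBLAST | 0.5 | −0.9 | −1.7 | −2.6 |
| Either | 0.12 | 0 | 0 | 0 |

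**False non-inferiority at a true difference of −10 points.** Success is 78% among HEMOBLAST-assigned and 88% among G+T-assigned subjects. The test is an unstratified Wald z = (difference + 0.10)/SE at the final look only, rejecting at z ≥ 2.036. Rates are summed over all binomial outcomes; simulations of 1,000,000 trials per case agree to about 0.1 point.

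| Case | k = 2 | k = 4 |
|---|---|---|
| No switches | 1.7% | 1.7% |
| HEMOBLAST to G+T, f = 0.3, by received | 2.1% | 2.6% |
| HEMOBLAST to G+T, f = 0.5, by received | 2.8% | 4.3% |
| HEMOBLAST to G+T, f = 1.0, by received | 4.9% | 12.0% |
| HEMOBLAST to G+T, same cases, as randomized | 1.7% | 1.6–1.7% |
| G+T to HEMOBLAST, f = 0.5, by received | 1.0% | 0.5% |
| G+T to HEMOBLAST, f = 1.0, by received | 0.4% | 0.1% |

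The 1.7% baseline is for one look at the final boundary. It is not the plan's overall 2.5%.

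**Two-look cross-check.** This uses the Table 9 efficacy boundaries and other assumptions: 1%, 2% or 5% of HEMOBLAST-assigned subjects (about 3, 5 or 13 of 267) receive G+T, with success in those bleeds 50% on G+T and 40% on HEMOBLAST. Type I error by device received is 0.047, 0.082 and 0.277. As randomized it is 0.027, 0.028 and 0.034.

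**As-randomized grouping is not automatically conservative.** With four non-selective switches, a true −10.0 becomes (263×0.78 + 4×0.88)/267 − 0.88 = −9.85 points (HEMOBLAST to G+T), or 0.78 − (129×0.88 + 4×0.78)/133 = −9.70 points (G+T to HEMOBLAST).

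**The case against.** The strongest defence is that the plan does not clearly call for a by-received primary test. The grouping sentence speaks of summaries, whereas the sentences before it in the same paragraph speak of analyses. Elsewhere the documents usually tie the word arm to randomization (Protocol 6.4.3, 6.4.5 and 12.2.6), so the methods sections could be read as as-randomized. This shows ambiguity, and I accept it. No passage settles it, however, and the multiplicity sections still describe the contrast as "in subjects receiving HEMOBLAST™ to those receiving G+T".

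Switching is also constrained. The assigned hemostat must be used, and reapplication is of the randomized product. Recothrom, the thrombin in G+T, is barred for HEMOBLAST-assigned subjects after 10 minutes and at other bleeding sites (Protocol 6.4.3, 6.4.4). Adding another hemostat before 6 minutes counts as failure (Protocol Table 8). In practice only a wrong device at first application matters, and that would be a deviation. This makes the problem unlikely but does not supply the missing estimate.

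Finally, every switching scenario is assumed. The main error rates are unstratified and single-look, mild selection gives only 2.1% to 2.6%, and the opposite direction lowers the error. As-randomized grouping can also dilute a true difference. All of that stands, and it is the reason for keeping the by-received analysis beside the as-randomized one.

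**Conclusion.** The concern holds. The only explicit grouping rule is by device received, the primary contrast is worded the same way, and no as-randomized hemostasis analysis is planned in either document. If the rule was meant for descriptive tables only, the plan has no stated rule for its primary test, and the same correction is needed.

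The effect is nil without switches and, in the equal-success calculation, nil when switching is unrelated to prognosis. When HEMOBLAST-assigned subjects with harder bleeds receive G+T, two to four switches are enough in the moderate and worst-case scenarios to take the false non-inferiority rate above 2.5%. Switches the other way make the test conservative. These results depend on assumed switch numbers and failure rates that the documents do not give. This should be corrected because it touches the sole success criterion, although the likelihood of harm is low.

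**What to change.** - In Protocol 12.2.1 and 12.2.4 and SAP 10.2 and 10.10, state that the primary and secondary hemostasis endpoints are analysed by randomized arm within the TTH Population, at the interim and final analyses.
- In Protocol 12.3.1.2 and SAP 10.5.2, define treatment arms in the same way.
- Limit the intervention-received sentence to safety.
- Pre-specify the by-received hemostasis analysis as a sensitivity analysis, because as-randomized grouping can dilute a true difference.
- Report the number of switches by randomized arm.

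The cost is wording in both documents and one extra table, and the change should be made before the interim analysis. The envelope number and treatment arm are already on the Intraoperative CRF (Protocol 6.4.5). The sample size of 400, the boundaries and the planned power are unchanged.

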12.2.2 Handling of Missing Data

In primary analyses, missing TTH values will not be imputed. All values right censored prior to 6 minutes will be considered treatment failures for the purpose of the primary analysis. Further sensitivity analyses for the impact of potential missing data will be defined in the Statistical Analysis Plan (SAP).

12.2.3 Subgroup Analyses

Descriptive analyses of safety and efficacy data will be presented by surgery type. The primary efficacy endpoint, as well as all secondary efficacy endpoints and safety outcomes will be presented by surgery type. Estimates of the distribution of TTH over a maximum follow-up of 10 minutes will be computed using the Kaplan-Meier method, stratified by surgery type. Kaplan-Meier estimates for the probability of continued bleeding at all scheduled assessment times (3 minutes, 6 minutes, and 10 minutes) will be displayed on each plot along with corresponding 95% confidence intervals. Additionally, the primary efficacy endpoint, as well as all secondary efficacy endpoints and safety outcomes will be presented stratified by:

- The number of interventions (separate applications of randomized hemostat);
- Baseline SBSS score; and
- Abnormal versus normal coagulation values.

The study will recruit patients undergoing elective surgery. Based upon this and the inclusion/exclusion criteria to be implemented, it is assumed that patients with abnormal coagulation studies will not be randomized and treated. In the unlikely event that patients with abnormal coagulation studies are present, a secondary analysis of the primary endpoint considering only those subjects with normal coagulation studies will also be conducted. Further, to assess the robustness of the primary endpoint with respect to possible imbalances in the frequency of patients with abnormal studies by treatment arm, a “worst-case” sensitivity analysis assuming all randomized and treated subjects in the HEMOBLAST™ arm with abnormal studies are treatment failures for the primary endpoint (TTH greater than 6 min) while all randomized and treated subjects in the G+T arm with abnormal studies are treatment successes (TTH less than 6 min). These subgroup and sensitivity analyses will be presented along with the primary results conducted on the TTH Population defined in Section 12.2.1.

12.2.4 Accounting for Multiple Comparisons

The primary analysis comparing the probability of TTH within 6 minutes in subjects receiving HEMOBLAST™ to those receiving G+T will be conducted to maintain an overall 0.025 (one-sided) significance level accounting for one interim analysis and one final analysis (see Sections 12.4.1 and

12.4.2). The exclusion of a >10% difference in the probability of TTH at 6 minutes will be indicated by the lower limit of a 95% confidence interval for the adjusted difference in binomial proportions (HEMOBLAST™ – G+T). All reported inference (confidence intervals and p-values) will account for the planned interim analysis.

Adjustment for multiple comparisons when assessing secondary endpoints will be performed using a fixed sequence closed testing procedure. The experiment-wise Type I error rate will be controlled in the strong sense at a (two-sided) 5% significance level. In a fixed sequence testing procedure, the formal inferential testing can proceed to the next step only when statistical significance is declared in the current step. If the testing sequence is stopped, the remaining endpoints in the testing sequence will be considered exploratory. Furthermore, any comparisons that are not presented in the a priori specified testing procedure will also be considered exploratory. The fixed sequence testing procedure will be employed among the primary and secondary endpoints in the order presented below:

- 1) Primary endpoint: Success at achieving hemostasis within 6 minutes for the first treated bleeding site (comparable efficacy of HEMOBLAST™ relative to G+T, evaluated using a 10% non-inferiority margin);
- 2) Secondary endpoint: The difference between arms in mean preparation time, defined as the time from the opening of package to product being ready to use (measured in minutes and seconds);
- 3) Secondary endpoint: Success at achieving hemostasis within 3 minutes for the first treated bleeding site (comparable efficacy evaluated using a 10% non-inferiority margin);
- 4) Secondary endpoint: Success at achieving hemostasis within 6 minutes for the first treated bleeding site (superiority of HEMOBLAST™ relative to G+T); and
- 5) Secondary endpoint: Success at achieving hemostasis within 3 minutes for the first treated bleeding site (superiority of HEMOBLAST™ relative to G+T).

